**Is this RCT adequately statistically powered?** In the study design, several factors were involved in determination of sample size. **First**, we drew estimated effect sizes from the **two** pilot studies on GCBT and from a recent meta-analysis (Bradley et al., 2005). Within the MVA pilot study, which contrasted GCBT with a minimal contact comparison condition, effect sizes for PTSD measures ranged from .83 to 1.04 (Hedges's unbiased  $g$ , Hedges, 1981). Within our Vietnam veteran pilot data, the pre-post treatment effect size for the PCL-M was  $d = 1.43$ . Consulting the larger literature, Bradley et al. (2005) computed average effect sizes (Cohen's  $d$ ) of .84 for contrasts between CBT versus supportive therapy conditions and 1.01 for contrasts between ET + cognitive therapy versus supportive therapy conditions. However, in RCTs involving veterans, effect sizes tend to be smaller, owing to the chronicity and severity of combat-related PTSD in this population. In computation of sample size for this trial, we have selected a relatively low value of  $d$  (.50); review of available studies (including our own pilot data) suggests effect sizes ranging from 0.84 to 1.43. Recognizing that effect sizes for contrasts between CBT and supportive psychotherapy tend to average  $d = .84$  (Bradley et al., 2005), that data from samples with chronic PTSD tend to have smaller effects, relative to less severe samples, and that effect sizes drawn from relatively small samples can be unstable, we took a conservative stance in estimating the effect size for the GCBT versus SGP contrast to arrive at  $d = .50$ . **Second**, because treatment within both conditions of this RCT will occur in groups, the analytic plan must account for the cluster effect owing to the correlation of outcomes within groups (expressed as  $\rho$ , the intraclass correlation coefficient). There is one clustered variable in this design (individuals within groups) which will be adjusted for in determining sample size. Following guidelines provided by Hsieh (1988) and Diggle et al. (2002), we used an inflation factor that was driven by the  $\rho$  values from the MVA-related PTSD pilot data. In particular, the  $\rho$  estimate of 0.11 is a conservative assumption, based on the largest value obtained in the pilot MVA study. In the pilot MVA study ([name] et al., 2009), the  $\rho$  for the CAPS was 0.07, the  $\rho$  for the BDI-II was 0.03, and for the BAI, the  $\rho$  was 0.08. Within the Collaborative 420 study (Schnurr

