
et al., 2003), the  $\rho$  for the CAPS was 0.05. Thus, use of  $\rho = 0.11$  in our power calculations is a conservative assumption. Larger values of the  $\rho$  can occur when the outcome measures (among patients) have a concrete connection to one another. In studies of physician behavior within a clinic, the  $\rho$  values are larger when the physician directly contributes to the assessment of the patient outcome measures. For example, Stedman et al. (2008) analyzed two such studies, one study of patients within selected clinics who were followed to determine if their clinic physician did or did not provide osteoporosis management, and a second study of patients within clinics to determine if physician education induced physicians to improve the quality of osteoporosis management. In each study the  $\rho = 0.12$ . The outcome measure for the patient was the level of disease management delivered by the physician, an outcome directly determined by the physician. In contrast, for our proposed study, the person who assesses patient outcomes should have little or no effect on the values of the patient measure outcome. In our study, the  $\rho$  captures a subtler effect, namely, potential assessor bias, a much smaller effect than the effect of physician practice patterns. With a proposed group size of 7, a maximum  $\rho$  of 0.11, and  $d = 0.50$ , we estimated a total  $n$  of 196, using  $p < .05$ . Although only two of 14 outcome variables in the pilot study exceeded  $\rho > .10$  (see [name] et al., 2009), we felt it was preferable to be conservative regarding  $\rho$  levels in our power computations. **Third**, in computation of sample size, we relied on .80 power level, as is customary in power calculations for RCTs. Using these parameters, the total desired  $n$  will be 196 ( $n = 98$  per condition); each treatment group will begin with 7 men. Thus, based on previous studies on Group CBT, as well as current data regarding ICC in the context of clinical trials, we have been appropriately conservative in our power calculations.

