In addition to statistical significance, we were concerned about the potential clinical significance of these data. Presently, there is no agreed-upon effect size that is thought to be clinically significant. This is difficult to determine because effect sizes hinge on many variables (e.g., the size and nature of the sample, the amount of variance in the assessment strategy, the amount of variance in treatment administration). In our power calculations, we have relied on a .80 power level, to have a sufficient sample size for this RCT for statistical significance. Unfortunately, there is no consensus in the treatment literature regarding what constitutes a clinically significant effect size; Friedman and colleagues (2006) suggest that clinically meaningful differences between 2 active treatments would be illustrated by an effect equal to or greater than .30 (Cohen's  $d$ ). Consultation with [name] (Project Statistician) thus indicates that the proposed  $n$  will be sufficient to determine whether GCBT produces clinically meaningful outcomes.

**Analytic approach:** Data from both sites will be combined prior to analyses. [name], the Project Statistician, will work in close collaboration with [name] to perform the analyses. Prior to testing hypotheses, the outcome data will be examined to assess if they meet the assumptions for the proposed statistics (Tabachnick & Fidell, 2001). If the assumptions are not met (e.g., the data depart from normality, multivariate outliers are present), appropriate data transformations will be used. Additionally, the GCBT and SGP groups will be examined for pre-treatment differences, to test for group equivalency. These analyses will involve a series of independent  $t$ -tests on each of the outcome measures as well as demographic variables. Pre-treatment differences between conditions will be incorporated into the models used to examine the primary hypotheses, as described below.

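### The planned 196 cannot settle whether a difference of d = .30 exists (35–45% two-sided power), and the stated inputs do not give 98 per arm

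*Combined protocol and SAP*

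**What the plan says.** The sample-size text (*Is this RCT adequately statistically powered?*) uses d = .50, groups of 7, an ICC of .11, p < .05 and .80 power, and arrives at 196 in total, 98 per condition. On power it says that "in computation of sample size, we relied on .80 power level, as is customary in power calculations for RCTs", and on group size that "each treatment group will begin with 7 men". The ICC "estimate of 0.11 is a conservative assumption, based on the largest value obtained in the pilot MVA study". The same text reports CAPS ICCs of .07 in that pilot and .05 in an earlier veterans' group-therapy trial. An inflation factor is mentioned without a formula, and the test is not said to be one- or two-sided.

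The next paragraph turns to clinical significance. It concedes that "Presently, there is no agreed-upon effect size that is thought to be clinically significant" and repeats that for the sample size "we have relied on a .80 power level, to have a sufficient sample size for this RCT for statistical significance". It then reports one published suggestion, that "clinically meaningful differences between 2 active treatments would be illustrated by an effect equal to or greater than .30". The following sentence concludes, as a consequence, that the planned n "will be sufficient to determine whether GCBT produces clinically meaningful outcomes". No power at .30 is given.

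The *Analytic approach* text expects some missing data but describes direct maximum likelihood as keeping an effective sample of 196.

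**The concern.** The conclusion is placed directly after the .30 benchmark and is worded as following from it, yet the sample was sized for an effect two-thirds larger. Required sample size varies with 1/d², so a trial sized at .50 needs (.50/.30)² = 2.8 times as many participants for the same power at .30.

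This matters most if the result is non-significant. The comparator is another active group treatment, and Section B.2 describes a 360-veteran group-therapy trial that found no difference between its arms. A reader relying on the sufficiency statement could take a non-significant result as evidence against a clinically meaningful difference when the trial had little chance of detecting one of .30.

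Separately, if 98 per arm does not follow from its stated inputs, the .80 claim at d = .50 may not hold either.

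**Working it through.** **Inputs.** From the sample-size text: d = .50, m = 7 per group, ICC ρ = .11 (CAPS values .07 and .05), α = .05, power .80, 98 per arm. From Hypothesis 1 in Section D.7.a: 14 groups per condition, so 28 − 2 = 26 between-group df. Benchmark: d = .30. The design effect 1 + (m − 1)ρ is my inference, since no formula is given. No missing data and no baseline adjustment are assumed.

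**1. The plan's own figure.**

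- Two-sided: n₀ = 2(1.960 + .8416)²/.50² = 62.79 per arm. The design effect is 1 + 6 × .11 = 1.66, so n = 104.2 (or 63 × 1.66 = 104.6).
- One-sided: n₀ = 49.46, so n = 82.1 (or 50 × 1.66 = 83.0).
- Neither gives 98. The inflation implied by 98 is 98/62.79 = 1.561 two-sided or 98/49.46 = 1.981 one-sided, against 1.66.
- The variant 1 + mρ = 1.77 gives 111 or 88.
- Two-sided, 98 is reached with groups of 6 (63 × 1.55 = 97.7), with ρ of about .093, or with ρ = .07 and a t-test on group df. None of these is what the text states.

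**2. Power with 98 per arm.** Effective n per arm is 98/1.66 = 59.04 (ρ .11), 98/1.42 = 69.01 (ρ .07) and 98/1.30 = 75.38 (ρ .05). The non-centrality is d√(n_eff/2). At d = .30 and ρ .11 it is .30 × √29.52 = 1.630, so two-sided normal power is Φ(1.630 − 1.960) = .371. The ranges below run from t on 26 df to the normal approximation.

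| ρ | d = .30, two-sided | d = .30, one-sided | d = .50, two-sided |
|---|---|---|---|
| .11 | 34.8–37.1% | 47.7–49.4% | 74.4–77.5% |
| .07 | 39.6–42.2% | 52.8–54.7% | 80.7–83.6% |
| .05 | 42.6–45.3% | 55.9–57.8% | 84.0–86.6% |
| 0 | 52.5–55.6% | 65.5–67.6% | – |

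One-sided power at d = .50 and ρ .11 is 84.1–85.8%. A simulation of 200,000 trials, with 14 group means per arm and a t-test on 26 df, gave .348, .394 and .424 two-sided at d = .30 for ρ = .11, .07 and .05.

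**3. Detectable effect and precision.**

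- Smallest d with .80 power, two-sided: .52–.54 (ρ .11), .48–.50 (.07), .46–.47 (.05).
- The same, one-sided: .46–.47, .42–.44, .41–.42. All are above .30.
- Two-sided 95% confidence interval half-width at ρ .11: 1.96 × √(2/59.04) = .361 SD, or .378 with t.
- For scale only, .80 power at d = .30 two-sided needs 2(1.960 + .8416)²/.30² = 174.4 per arm before inflation. In total that is 579, 495 or 453 for ρ = .11, .07 or .05 (one-sided 456, 390 or 357).

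**The case against.** **The sentence may be making a weaker claim.** The paragraph admits there is no consensus, reports .30 as one suggestion and never adopts it as a target. It could mean only that the design effect of .50 exceeds .30. It could also mean that any significant result will show an estimate above .30, since the smallest estimate significant two-sided is .36–.38 at ρ .11 and .32–.33 at ρ .05. Both statements are true. Neither makes the sample able to determine whether a difference of .30 or more exists, which is what the text concludes.

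**The planned model may do better than the unadjusted calculation.** The growth model includes the pre-treatment score, and regression of slope on intercept is offered as one way to handle baseline differences. The documents give no pre–post correlation r, so any gain is an assumption. With covariance-type adjustment, two-sided power at d = .30 over ρ .11–.05 would be 44–57% at r = .5 and 59–73% at r = .7. Reaching .80 would need r of about .75–.83. Without that regression, the slope contrast behaves like a change score, whose variance factor 2(1 − r) is below 1 only if r exceeds .5. What stands is that the unadjusted figures must be labelled as such, and that the chance of missing .30 could fall below one half in the adjusted model.

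**The 98 may rest on a different formula.** The inflation factor is attributed to cited references that are not reproduced. That is fair, so the firm finding is that sidedness and formula are unstated and the usual formula does not give 98. The two-sided shortfall is modest. An r of about .24 (normal) or .36 (t) would restore .80 at ρ .11.

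**Missing data are largely handled.** Follow-up of dropouts and not-missing-at-random sensitivity analyses are planned, so the effective-N wording is a minor point.

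**Conclusion.** The concern holds. On the design's own inputs, the sufficiency conclusion does not follow from the only benchmark cited. Power at d = .30 is 35–45% two-sided and 48–58% one-sided over ICCs of .11 to .05, and below .80 even with no clustering, so this result does not depend on the inferred inflation formula. At ρ .11 a non-significant result may not exclude .30.

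The second part also holds but is smaller. Under the usual design effect, the stated inputs do not produce 98 per arm. If the test is two-sided, the .80 claim fails at ρ .11 (74–78%) but is met at the reported CAPS ICCs. If it is one-sided, the claim is met at ρ .11 as well.

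All figures assume complete data and no baseline adjustment. Missing outcomes would lower them, and a strong pre–post correlation would raise them. This should be fixed, but it does not call for a redesign.

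**What to change.** Keep N = 196.

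1. In the clinical-significance paragraph, replace the sufficiency sentence with:

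> The trial is sized for d = .50. Power at the suggested benchmark of d = .30 is about 35–37% at ICC .11 and 40–42% at ICC .07 (two-sided), before missing data and without baseline adjustment. A non-significant result may not exclude a difference of .30 (95% CI half-width about 0.36–0.38 SD at ICC .11).

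   If the planned test is one-sided, use 48–49% and 53–55% for power and say so. If the sentence was meant only to note that .50 exceeds .30, it should say that instead.

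2. In the sample-size text, state the sidedness and the inflation formula actually used, and restate power to match. On the usual formula, two-sided power is about 74–78% at ICC .11 and 81–84% at ICC .07, and one-sided power is 84–86% at ICC .11. Alternatively, base the .80 claim explicitly on the pilot CAPS ICC of .07.

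3. In *Analytic approach*, say that direct maximum likelihood includes all 196 randomized participants, not that it keeps an effective N of 196. If power under missing outcomes is added, label the missing rate as an assumption.

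The changes are to wording only, with design and analysis untouched. The cost is a less favourable statement about d = .30.

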extent of dependency (i.e., clustering) by calculation of intraclass correlations (ICCs) using variance estimates from unconditional cell means models of key outcome variables (cluster = treatment group). Our proposed  $N$  of 196 will be clustered into 14 treatment groups per condition. Assuming non-zero ICCs, a multilevel approach will be incorporated into the latent growth framework in order to obtain correct standard errors, test statistics, and confidence intervals. In the traditional multilevel modeling, the design would be construed as a three-level model; i.e., repeated observations (Level 1) nested under individuals (Level 2), individuals nested under treatment groups (Level 3). However, because the first two levels are combined in the multivariate framework of latent growth modeling, this design can be characterized as a two-level model (i.e., latent growth factors are nested under treatment groups) where time-invariant covariates (i.e., dummy codes for treatment condition) are included to account for the within-group and between-group variability in initial status (pre-treatment) and symptom change (improvement over active treatment and follow-up). In the latent growth model portion of the models, the intercept will be centered on pre-treatment (i.e., first slope loading will be fixed to 0.0). Because there is no substantive interest in the form of the growth trajectory, intermittent time points (i.e., slope factor loadings) will be freely estimated and the final timepoint of interest (e.g., post-treatment) will have a corresponding factor loading fixed to 1.0. Accordingly, the mean and variance of the slope will convey the fixed (average) and random effects (individual differences) of change for the given time interval of interest. The Level 2 variables of treatment condition (single dummy code using *SGP* as reference group) will be included as predictors to account for individual differences in treatment response and variability in outcome across treatment groups. To examine pre-treatment differences between treatment conditions, the intercept (centered on pre-treatment) will be regressed onto the treatment covariates (i.e., significant paths are indicative of differences in pre-treatment levels as a function of treatment condition). Any pre-treatment differences will be accommodated into the interpretation of findings and in the parameterization of the models (e.g., regression of the slope onto the intercept, as well as covariates such as treatment condition). The dependent variable for this analysis is the CAPS total score. Additionally, PCL will be examined, using the same analytic approach, in order to examine respondent effects (interviewer-rated versus self-report).

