
***Hypothesis 2.*** Reductions in PTSD symptom severity will be maintained in the GCBT group at 12-month follow-up. Much as with Hypothesis 1, multilevel latent growth modeling will be used. In the analyses to examine Hypothesis 2, we will not include the treatment condition covariate but will include the site dummy code, to examine potential site differences. To test the prediction that the means of 6mos and 12mos do not differ, the slope factor loadings corresponding to these two time points will be constrained to equality and compared to the fit of a latent growth model where the 6 mo time point was freely estimated ( e.g., Baseline model:  $0^{* * 1}$ ; hypothesized model:  $0^{* * 1} 1$ ).

The **secondary aim** is to examine the generalizing effects of both GCBT and *SGP* on co-morbid conditions, distress and impairment. Because most trials in the PTSD literature do not include a thorough assessment of treatment generalization, it is unknown whether available treatments only address PTSD or whether gains generalize to related domains of functioning, including co-

morbid conditions such as depression, generalized anxiety, and alcohol use. Three hypotheses are proposed:

**Hypothesis 3.** For patients who are diagnosed with co-morbid Major Depressive Disorder (MDD), Generalized Anxiety Disorder (GAD), and/or Alcohol abuse prior to treatment, GCBT will produce significantly larger symptom reductions for these conditions, relative to SGP at post-treatment assessment and these generalized changes will show stability at 6 mo follow-up (FU). To test this hypothesis, we will use multi-level analysis, as discussed for Hypothesis 1. For continuous variables (BAI, BDI-II, SIP), we will use the same approach as described for Hypothesis 1. Although latent growth modeling can accommodate categorical outcomes (e.g., MDD+, MDD-) with an appropriate estimator (e.g., robust weighted least squares, maximum likelihood with numerical integration), there is concern about the estimation failure resulting from low cell frequencies, particularly at post-treatment and follow-up. In the event that cell frequencies are too low, we will augment the analyses from the continuous variables with more descriptively oriented statistics showing the rates of comorbidity decline at each assessment point as a function of treatment condition.

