**Hypothesis 4.** Patients who receive GCBT will report less distress and impairment, relative to patients who receive SGP, at post-treatment assessment, a between-group difference that will persist through 6 month follow-up. To test this hypothesis, we will use multi-level analysis, as discussed for Hypothesis 1. For continuous variables (SF-36 subscales), we will use the same approach as described for Hypothesis 1.

**Hypothesis 5.** Gains in these domains (distress and impairment) will be maintained in the GCBT group at 12-month follow-up. To test this hypothesis, we will use multilevel latent growth modeling, using the same approach as discussed for Hypothesis 2.

**D.7.d. Secondary data analyses:** In addition to analyses designed to test these hypotheses, several secondary analyses will be conducted. **(1). Diagnostic and reliable change status:** In order to facilitate comparison with other RCTs, we will compute the percentage diagnosed with PTSD for both GCBT and SGP at post-treatment and , 3- and 6- mo follow-up. To determine reliable change, we will follow guidelines outlined by Jacobson and Truax (1991). Specifically, the reliable change index utilizes both the reliability of measurement device, along with a confidence interval, to determine reliable change. We will utilize CAPS Total scores and a stringent confidence interval (95%) to determine reliable change scores within both the GCBT and SGP conditions, at post-treatment and 6 mo follow-up assessment.

**(2). Examine the generalizing effects of both GCBT and SGP on healthcare utilization.** We will examine the effect of PTSD group treatment on healthcare utilization. We expect that veterans who receive GCBT will display less health care utilization relative to veterans who receive SGP. We will use the same multilevel analysis approach described above (with number of health care visits as the continuous variable).

**(3). Predictors of individual differences in outcome:** Although the primary aims of this RCT do not include a focus on individual differences that may affect outcome, we propose analyses to look at select variables in this regard. Recognizing that these are exploratory, we propose to look at (1) the number of sessions attended, (2) group psychotherapy alliance (four

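### H1, H3 and H4 adjust for the baseline outcome only when a pre-treatment difference is found; always adjusting needs no new data and would save about 0–11% of variance

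*Combined protocol and SAP*

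**What the plan says.** The Analytic approach section plans independent t-tests between arms on every outcome measure and on demographic variables. It continues: "Pre-treatment differences between conditions will be incorporated into the models used to examine the primary hypotheses".

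D.7.a, Hypothesis 1, regresses both the intercept (centred on pre-treatment) and the change factor on condition. Of the intercept regression it says that "significant paths are indicative of differences in pre-treatment levels as a function of treatment condition". It then says: "Any pre-treatment differences will be accommodated into the interpretation of findings and in the parameterization of the models". Regressing the slope on the intercept is offered as an example of how to do this.

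The same approach carries over to two secondary hypotheses. For H3: "For continuous variables (BAI, BDI-II, SIP), we will use the same approach as described for Hypothesis 1". For H4: "For continuous variables (SF-36 subscales), we will use the same approach as described for Hypothesis 1". H2 and H5 test maintenance within the GCBT arm, have no between-arm contrast, and are not part of this point.

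No section makes adjustment for the baseline outcome a fixed part of the between-arm model.

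**The concern.** Under randomisation, a baseline test at 5% is significant in about 5% of trials whatever the true treatment effect. It is therefore a poor guide to whether the baseline value should be in the model. What matters is how strongly baseline predicts outcome.

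Two things are at stake. The first is prespecification: with no alpha, two possible triggers and only an example of the adjustment, two analysts could fit different primary models to the same data. The second is precision: when the trigger does not fire, the intercept is still free to differ by arm, so the treatment effect on the slope is close to a raw difference in change. In large samples that is never more precise than adjusting for the observed baseline.

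**Working it through.** **The plan's own figure.** The documents give no precision figure for baseline adjustment. The nearest is the sample size of 196 for d = .50, ICC .11, groups of 7, p < .05 and power .80. Using 2(1.96 + .84)²/.5² = 62.8, so 63 per arm, and a design effect of 1 + 6 × .11 = 1.66, I get 105 per arm, or 210. At 98 per arm, power is .775 (normal) or .744 (t on 2 × 14 − 2 = 26 df). That shortfall is a separate matter. It matters here only because the power calculation has no slack and takes no credit for baseline.

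**Inputs.**
- ICC: .11 (power section). For comparison, the same section reports that the pilot value "for the CAPS was 0.07", and gives .05 for the earlier VA cooperative study of group therapy.
- k = pre SD / post SD, pooled over arms from the pilot tables in C.2: CAPS avoidance/numbing 7.10/10.72 = .66; CAPS hyperarousal 6.13/7.95 = .77; BDI-II 9.11/11.33 = .80; PCL-M 9.47/11.46 = .83. CAPS total SDs are not in the available text.
- r = pre-post correlation: not stated. I assume .3, .5 and .7.

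**Formulas** (post SD = 1; clustering assumed to arise after baseline):
- Always adjusted: V_adj = 1 − r² + 6·ICC.
- Change score: V_change = V_adj + (k − r)².
- 5% check, then adjust: the share of the excess that is kept is .95 − 2(1.96)φ(1.96) = .72, so V_plan = V_adj + .72(k − r)².

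**Results at ICC .11.**

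| r | k | V_adj | V_change | V_plan | Saved vs never adjusting | Saved vs 5% check |
|---|---|---|---|---|---|---|
| .3 | .66 | 1.570 | 1.700 | 1.663 | 7.6% | 5.6% |
| .3 | .83 | 1.570 | 1.851 | 1.773 | 15.2% | 11.4% |
| .5 | .66 | 1.410 | 1.436 | 1.428 | 1.8% | 1.3% |
| .5 | .83 | 1.410 | 1.519 | 1.488 | 7.2% | 5.3% |
| .7 | .66 | 1.170 | 1.172 | 1.171 | 0.1% | 0.1% |
| .7 | .83 | 1.170 | 1.187 | 1.182 | 1.4% | 1.0% |

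Against the 5% check, the range is 0–13% at ICC .07 and 0–14% at ICC .05. If pre and post SDs were equal, it would be 5–18% at ICC .11.

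**Power** (ncp = .5/√(2V/98), t(26), k = .83, ICC .11), for never adjusting, 5% check and always adjusting: r = .3, .70, .72, .77; r = .5, .78, .79, .81; r = .7, .871, .872, .876.

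**Simulation** (8,000 trials, 14 groups of 7 per arm, ICC .07, k = .83, r = .5). Always adjusting saved 8.4% against never adjusting and 6.2% against the check (formulas: 8.5% and 6.3%). The check fired in 4.7% of trials. Null rejection was .052 (never), .050 (check) and .050 (always).

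**What the pilot says about r.** The C.2 statistics disagree.
- PCL-M, from F(1,21) = 10.64: the difference in change is 14.00 + 2.84 = 16.84, the SD of change is 12.37, and r = .31.
- PCL-M, from the paired p = .001 within GCBT (n = 11): t = 4.59, the SD of change is 14.00√11/4.59 = 10.12, and r = .69.
- BDI-II, from F = 8.54: SD of change 7.165, r = .78. From the paired p = .075: SD of change 10.566, r = .69. These cannot both hold, because 10 × 10.566² = 1,116 already exceeds the total of 21 × 7.165² = 1,078 and leaves a negative sum of squares for the control arm.

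**The plan's example form.** I approximate slope on latent intercept by the coefficient r/(k × reliability), which adds r²(1/reliability − 1)² to V_adj. At ICC .11 and k = .83, with assumed reliability .8 or .7, the saving against never adjusting is 14.9% or 14.3% at r = .3 (observed baseline 15.2%), 6.1% or 4.1% at r = .5 (7.2%), and a loss of 1.2% or 6.2% at r = .7 (a saving of 1.4%).

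**The case against.** The plan never uses the word only. Its promise to accommodate any pre-treatment differences could be read as adjusting for whatever difference is observed, which would amount to always adjusting. That reading is possible, but the t-tests and the reference to significant paths point to a test first. If unconditional adjustment is meant, the plan should say so.

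A reader might take 0–15% as what the plan loses. It is not: that figure is against never adjusting, which is not the plan. A 5% check recovers about 28% of the excess, because it adjusts in the trials with the largest imbalance. Even the 0–11% rests on an assumed alpha.

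A reader might also take the PCL-M value of r = .31 as evidence that the gain is near the top of the range. The pilot does not support that: another statistic for the same scale gives .69, where the saving against never adjusting is about 0–2%.

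For the CAPS the gain may be smaller still. D.3 expects a restricted pre-treatment range, and otherwise stratifies on the CAPS. The excess (k − r)² equals k²(1 − b)², where b = r/k is the slope of post on pre. For a given b, a restricted baseline shrinks the excess, and stratification removes most of the imbalance that adjustment would correct.

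Finally, a reader might infer that slope on intercept is an unacceptable form of adjustment. On the approximation above it recovers most of the gain at low to moderate r. It loses only at high r with imperfect reliability, where little is at stake.

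**Conclusion.** The point stands as a minor one on prespecification and efficiency. Adjustment for the baseline outcome in H1, and in H3 and H4 for continuous outcomes, depends on a data-driven check whose alpha, governing test and form are left open.

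A reader might infer bias or an inflated type I error. Neither follows: allocation is random, and simulated null rejection under the check was .050.

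Against the plan read as a 5% check-then-adjust rule, always adjusting saves about 0–11% of variance at ICC .11. This rests on SD ratios from small pilots, an assumed r of .3 to .7, clustering that arises after baseline, and a two-wave approximation to a growth model that also uses mid-treatment data. The gain is near nil at r of about .7. The prespecification argument holds whatever r turns out to be.

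**What to change.** Stop using baseline tests to choose covariates. In every H1, H3 and H4 model of a continuous outcome, prespecify adjustment for the baseline value of that outcome whatever the imbalance, and keep the therapy-group term. Report baseline comparisons descriptively.

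The preferred form models the mid-treatment, post-treatment and follow-up scores with the observed baseline as a covariate. A smaller change, also acceptable, is to make the plan's own slope-on-intercept regression unconditional. It captures most of the gain when r is low to moderate but may lose slightly when r is high and reliability is imperfect.

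The cost is a change to the analysis plan. The preferred form also respecifies the growth model, because the pre-treatment score moves from outcome to covariate. The baseline values are already scheduled for collection before randomisation, so no new data, visits or participants are needed.
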